1 PROTOCOL SYNOPSIS

Study Title:	Safety and Efficacy Study of the Neurent Medical NEUROMARK™ System in Subjects with Chronic Rhinitis
Short Title:	CLARITY Study
Study Device:	Neurent Medical's NEUROMARK™ System
Device Description:	
The NEUROMARK™ System is comprised of two (2) key devices; (1) a hand-held device designed to deliver Radio Frequency (RF) energy to soft tissue in otorhinolaryngological [also known as Ear, Nose and Throat (ENT)] procedures designed to interrupt nasal nerves aimed to reduce symptoms related to Chronic Rhinitis and (2) an algorithmically controlled low power radiofrequency Console (RFG) for delivery of RF energy to the device.
 
Refer to the Investigator's Brochure, provided as Appendix A, for additional details.

Study Objective:	The primary objective of this study is to evaluate the safety and efficacy of the Neurent Medical NEUROMARK™ System in patients that suffer from Chronic Rhinitis.
Study Design:	A prospective, single-arm, multicenter clinical Study to evaluate the safety and efficacy of the NEUROMARK™ System in patients with Chronic Rhinitis.
Study Size:	
This study aims to evaluate a total of thirty-six (36) study subjects at up to four (4) study centers. All subjects who meet the inclusion and exclusion criteria will receive treatment.
 
It is anticipated that approximately 15 subjects will be enrolled at each site. There is no enrollment maximum per site; however, no investigator may enroll more than 50% of the study population.

Subject Population:	Male and female patients in good general health who experience chronic rhinitis will undergo an initial screening. Those who provide written informed consent and meet eligibility criteria will be considered for enrollment.
Study Procedure:	Subjects that provide informed consent and meet study eligibility requirements will receive undergo treatment. Subjects will have the NEUROMARK™ System applied to both nostrils during a single session. The study procedure will be performed following the NEUROMARK™ System Instructions for Use (IFU), Appendix B .

Study Visits:	
All subjects will be evaluated at baseline, during treatment, immediately post-treatment, and at 24-48 hours, 1- month, 3- months, 6-months, 9-months and 1-year post treatment.
 
Refer to Table 1 for an overview of tests, procedures and other activities the subject will undergo as part of this clinical study.

Study Endpoints:	
Safety will be evaluated based on frequency of Serious Adverse Events (SAEs) directly attributable to the NEUROMARK™ System at one (1) month post index procedure.
 
Efficacy will be assessed by the change in Visual Analog Scale (VAS) Nasal Symptom Score (NSS) from baseline through 3 months for rhinorrhea and nasal congestion.

Additional Evaluations:	
Additional information, as listed below, will be collected and the resulting data analyzed and reported for each follow-up, as applicable.
 
• A change in the VAS NSS from baseline.• A change in reflective Total Nasal Symptom Score (rTNSS) from baseline for rhinorrhea.• A change in rTNSS from baseline for nasal congestion.• A change in rTNSS from baseline.• A change in Postnasal Drip (PND) from baseline.• A change in Quality of Life (mini-Rhinoconjunctivitis Quality of Life Questionnaire (RQLQ) from baseline.• Procedure tolerability (e.g., discomfort, length of procedure)• Individual symptoms (e.g., post-nasal drip, nasal itching, sneezing)• Responder rates.• Patient satisfaction (e.g., patient reported symptom relief)• Endoscopic assessment.• Post-procedure discomfort (e.g., headache, facial pain, ear pain/blockage).• All adverse events regardless of severity or relatedness. 
All subjects who undergo treatment will be followed to 1 year for informational purposes and any study related findings will be reported.

Anticipated Duration:	
The study is anticipated to begin enrollment in Q1 of 2022 with enrollment complete in Q2 of 2022. The last patient visit is expected to take place by or during Q2 of 2023.

Study Evaluations:	Table 1 provides an overview of all protocol-related activities the Subject can expect to undergo as part of study participation.
Indications for Use	The NEUROMARK™ System is indicated for use in otorhinolaryngology (ENT) surgery for creation of radiofrequency (RF) lesions to disrupt posterior nasal nerves in patients with chronic rhinitis.
Intended Use:	The NEUROMARK™ System is intended for the application of Radiofrequency energy to create lesions in mucosal tissue in otolaryngological [also known as Ear, Nose and Throat (ENT)] procedures in patients with chronic rhinitis.

Screening Considerations:

- If data are available at baseline and the information collected per protocol, the existing data may be used to support patient screening. The test/assessment may not need to be redone.
- If Subject is ill or experiencing an exacerbation of symptoms due to illness, the protocol required assessment or follow up visit may be postponed without a protocol deviation. If this occurs, the illness and reason for postponement must be documented in the Subject's study records.
- If a study subject has been exposed to COVID-19 requiring quarantine or isolation or has traveled to a location(s) that may require quarantine, the follow up will be performed outside of the allowable window and the reason documented. This will not be considered a protocol deviation.

Table 1: Study Related Tests, Procedures and Activities**X = Require O = Optional**

	Screening	Immediately Pre-treatment Procedure	Immediately Post-Treatment	24– 48 Hour (phone or in-clinic)	1-Month (±7 days)	3-Month (± 14 days)	6- Month Follow-up (± 14 days)	9-Month Follow-up (± 14 days)	1 Year Follow-up (± 14 days)
Informed Consent	X								
History & Demographics	X								
Inclusion/Exclusion Criteria	X								
Pregnancy Test (if	X								
Physical Exam (including Blood Pressure)	X	X							
Computed Tomography (CT) Scan ^{1,2}	X								
Evaluation of Nasal Cavity by Endoscopic	X	X			X	X			
NEUROMARK Treatment		X							
VAS NSS	X				X	X	X	X	X
rTNSS	X				X	X	X	X	X
Mini-RQLQ	X				X	X	X	X	X
COVID-19 Test for Active Infection ⁵	X	O			O	O	O	O	O
Evaluation of Procedure and Anesthesia Tolerability			X	X					
Patient Satisfaction					X	X	X	X	X
Concomitant Medications	X	X		X	X	X	X	X	X
Evaluation of Adverse			X	X	X	X	X	X	X
Study Exit									X

- 1 CT scans will be collected should a subject undergo evaluation for sinusitis during the follow up phase. CT scan at baseline is to rule out sinusitis. An existing CT scan may be used for the baseline assessment so long as it was performed within 6 months prior to treatment, and the subject's symptoms have remained stable. It is of note that subjects with sinusitis at baseline are excluded.
- 2 A Lund-Mackay Score should be assigned to each of the 12 sinuses. The sum of all scores is the Lund-Mackay Score.
- 3 A Lund-Kennedy score should be assigned to each nostril.
- 4 Should endoscopy be performed during active screening or at any time during the follow up phase, a recording will be provided to the sponsor.
- 5 A COVID-19 test for active infection is required prior to treatment. The COVID-19 test for active infection will also be performed if the Subject is suspected to be symptomatic for COVID-19 at any point during the study. This requirement is based upon availability of test units assuming there is not a shortage of test units. Should there be a shortage, subjects will be managed for their symptoms per current policy and the suspected infection documented and recorded in their study records.

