3.3 Device Operation

The device will be connected to the Console via a flexible electrical cable. The patient will sit in the surgery chair and local anesthetic is administered. The device is inserted into the nasal cavity under endoscopic guidance. For this part of the procedure, the end effector is constrained with only the shaft of the device tracking to the target position (**Figure 5**).

[figure not shown]

Figure 5: Introduction of the device into the nasal cavity - the end effector is not yet deployed.

Under endoscopic guidance, the physician will advance the device towards the posterior superior/inferior region of the nasal cavity. The visual shaft markings on the top and bottom of device shaft are aligned to ensure superior orientation within the nasal cavity during delivery. The physician will align the inter stage marker on the shaft at the lateral attachment of the middle turbinate thus ensuring that the device is correctly positioned prior to initiating deployment of the end effector (see **Figure 6**)

[figure not shown]

Figure 6: Device positioned in the correct target position prior to deployment of the end effector

Once in position, with the surgical landmark of the lateral attachment of the middle turbinate, the physician will move the slider proximally on the handle to the deployed position, thereby deploying the end effector in the nasal cavity (Figure 7: Device in position with end effector deployed. **Figure 7**).

[figure not shown]

Figure 7: Device in position with end effector deployed.

Once the end effector is deployed, and positioning within the cavity is correct, the electrical activation button on the device handle is pressed to assess the tissue bio-impedance. This impedance check provides confirmation of apposition of the electrodes against the lateral wall.

Upon completion of the impedance check, the NEUROMARK™ Console GUI will confirm to the user that they can initiate treatment. To deliver the therapy, the NEUROMARK™ device is activated by pressing down and holding the activation switch on the handle for 2 seconds. Radiofrequency energy will be delivered through the electrodes to create micro-lesions (**Figure 8**).

[figure not shown]

Figure 8: Energy delivery and lesion creation

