6.1 Procedure

The NEUROMARK™ procedure will be performed following the system's Instructions for Use (IFU) found in **Appendix B**.

Immediately prior to system introduction the Subject will have a local anesthetic administered to the target site per the clinic's standard practice. The local anesthetic used and related procedure will be documented in the Subject's file. Once the Subject is appropriately anesthetized, the NEUROMARK™ procedure may start. Both nasal cavities will be treated during a single treatment session.

Once both nasal cavities have been treated the system will be removed and the procedure will be considered complete.

The procedure may be photographed or videotaped. The Subject's identity will be concealed and patient confidentiality will be maintained.

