8.2 Assessment of Relationship

The Investigator will use the following definitions to assess the relationship of the AE to the use of the NEUROMARK™ System.

The Investigator will determine if the adverse event is related to the study procedure, the investigational device and/or a pre-existing condition as described below (**Table 5**).

Table 4: Adverse Event Relationship

AE Related to:	Description
Study Procedure	An AE that is the result of / or related to the study procedure but not necessarily the NEUROMARK™ System..
Investigational Device	An AE that is a result of / or related to use of the NEUROMARK™ System.
Pre-existing Condition	An AE that is a result of / or related to a pre-existing condition or injury.

The Investigator will then determine the adverse event relationship to the study device and the relationship to the study procedure as described below (**Table 5**) and (**Table 7**).

Table 5: Adverse Event (AE) Device Relationship

Relationship	Description
Not Related	
 → not associated with study device → due to an underlying or concurrent illness or effect of another device or drug
Unlikely	
 → little or no temporal relationship to the study device and/or → a more likely alternative etiology exists
Possible	
 → temporal sequence between device application and event → is such that the relationship is not unlikely or → Subject's condition or concomitant therapy could have caused the AE
Probable	
 → temporal sequence is relevant or → event abates upon device application completion/removal or → event cannot be reasonably explained by the Subject's condition
Highly Probable	
 → temporal sequence is relevant and → event abates upon device application completion/removal or reappearance of the event on repeat device application
Related	
 → temporal sequence is relevant and → the adverse event is directly related to the use of the NEUROMARK™ System

Table 6: Adverse Event (AE) Procedure Relationship

Relationship	Description
Not Related	
 → not associated with study procedure → due to an underlying or concurrent illness or effect of another device or drug

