Unlikely	
 → little or no temporal relationship to the study procedure and/or → a more likely alternative etiology exists
Possible	
 → temporal sequence between procedure and event → is such that the relationship is not unlikely or → Subject's condition or concomitant therapy could have caused the AE
Probable	
 → temporal sequence is relevant or → event abates upon procedure completion or → event cannot be reasonably explained by the Subject's condition
Highly Probable	
 → temporal sequence is relevant and → event abates upon procedure completion/removal or reappearance of the event on repeat device application

Relationship	Description
Related	→ temporal sequence is relevant and → An adverse event that is not directly related to the use of the NEUROMARK™ System but is directly attributable to the procedure in which Neuromark was used.

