10.2 Potential Risks

Refer to the manufacturer's labeling for details concerning potential AEs associated with the use of materials, tools or fluid used during the procedure or immediately post-procedure.

Potential risks to the study Subject that may be associated with the use of the NEUROMARK™ System are as follows. Risk of these events is low.

- Allergic or other reaction to device materials or anesthetic (subjects are to be excluded if an allergy/potential allergy is known)
- Trauma to the nasal cavity including

- Mucosal bleeding
 - Mucosal damage
 - Pain/discomfort
 - Synechiae/Adhesions
 - Perforation
- Infection
- Impaired Nasal Function including:
 - Olfactory change
 - Worsening nasal obstruction
 - Septal perforation
 - Worsened eustachian tube function
 - Cosmetic deformity
- Atrophic rhinitis or dry nose
- Headache
- Bone necrosis
- Burn

There may be additional risks related to the local anesthetic including dermal allergic reactions, itching, rash, erythema, stinging and inflammation. Many of these side effects will subside quickly. Systemic side effects are rare and unexpected. They include arrhythmia, hypotension, and a system allergic reaction.

There may be risks related to any post-procedure medication prescribed by the Study Investigator. Those risks can be found on the medication's labeling from the manufacturer.

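### The only safety endpoint counts SAEs attributed to the device, so a serious event assigned to the procedure alone stays outside the headline result, although it is reported elsewhere

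*Combined protocol and SAP*

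**What the plan says.** The Study Endpoints row of the synopsis (Section 1) gives one safety endpoint, the "frequency of Serious Adverse Events (SAEs) directly attributable to the NEUROMARK™ System at one (1) month post index procedure". The stated objective is in the same section: "The primary objective of this study is to evaluate the safety and efficacy of the Neurent Medical NEUROMARK™ System in patients".

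Section 8.2 separates two sources of harm. Table 4 describes a procedure-related event as "An AE that is the result of / or related to the study procedure but not necessarily the NEUROMARK™ System". Table 5 grades the relationship to the device and Table 6 the relationship to the procedure. The top grade of Table 6 reads: "An adverse event that is not directly related to the use of the NEUROMARK™ System but is directly attributable to the procedure".

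The procedure is part of every treatment. Section 6.1 states: "Immediately prior to system introduction the Subject will have a local anesthetic administered to the target site". Section 3.3 states: "The device is inserted into the nasal cavity under endoscopic guidance". Section 10.2 lists systemic effects of the anesthetic ("They include arrhythmia, hypotension, and a system allergic reaction"), describes them as rare, and gives no rate.

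Four other provisions bear on the point:

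- The Additional Evaluations row of the synopsis commits to reporting every adverse event, whatever its severity or cause.
- The study-exit rule in Section 6.5 names device and procedure together.
- Section 8.1 says that events before the System is used go into the medical record and do not count as related to either device or procedure.
- Section 5 treats a subject as enrolled only after treatment, and Section 11 builds the safety analysis on treated subjects.

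**The concern.** A patient who accepts this treatment accepts the anesthetic and the endoscopy with it. A serious reaction to either is a harm of being treated, yet the endpoint on which safety is to be judged leaves it out if the investigator assigns it to the procedure and not to the device. In an open, single-arm study, that one attribution decides whether a serious event appears in the headline figure. The documents supplied describe no independent adjudication of relatedness. The exit rule shows that the protocol can pair device and procedure when it wishes to, and no reason is given for not doing so in the endpoint.

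At stake is how the headline safety rate reads. At this sample size a single event moves it visibly.

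**Working it through.** **Inputs.** The endpoint is in Section 1, the relatedness grades in Section 8.2, the rule on events before device use in Section 8.1, the enrollment definition in Section 5, the safety set in Section 11 and the sample size in Section 11.2. The documents give no SAE rate, so every rate below is an assumption.

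**Step 1: where each kind of SAE falls.**

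| SAE within 1 month | In the endpoint as written? | In a device-or-procedure endpoint? |
|---|---|---|
| Rated Related to the device (Table 5) | Yes | Yes |
| Rated Related to the procedure (Table 6), not attributed to the device | No | Yes |
| After device introduction, rated Possible or Probable on Table 5 | Not determined: the plan does not say which grades count | Depends on the grades named |
| After anesthetic, before device use | No | No, unless Section 8.1 is changed |
| As above, and treatment is abandoned | No; the subject may also fall outside the safety set | No, unless Sections 5, 8.1 and 11 are reconciled |

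The second row is the core of the point. It follows from the endpoint wording set beside Table 6. The last two rows show that editing the endpoint sentence alone would miss part of the anesthetic risk.

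**Step 2: the plan's own figure.** Section 11.2 starts from 30 subjects and allows for 20% loss: 30 × 1.2 = 36, as stated. Dividing instead gives 30 / (1 − 0.20) = 37.5, rounded up to 38. The difference does not matter here. The plan gives no inputs for the 30. I use n = 36 treated subjects as the denominator.

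**Step 3: effect of an omitted event.** Limits are exact (Clopper-Pearson), two-sided 95%, counting subjects and assuming no device-attributed SAE.

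- 0/36: upper limit = 1 − 0.025^(1/36) = 0.0974, so 0% (0 to 9.7%).
- 1/36 = 0.0278: lower limit = 1 − 0.975^(1/36) = 0.0007; upper limit = 97.5th percentile of Beta(2, 35) = 0.1453. So 2.8% (0.07% to 14.5%).
- 2/36 = 0.0556: 5.6% (0.7% to 18.7%).

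Each subject left out lowers the headline by 1/36 = 2.8 percentage points. The endpoint can never exceed the device-or-procedure rate.

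**Step 4: chance that at least one such event occurs and is omitted.** With an assumed procedure-only SAE rate p, the chance is 1 − (1 − p)^36.

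| Assumed p | Chance of at least one among 36 |
|---|---|
| 0.1% | 1 − 0.999^36 = 3.5% |
| 0.5% | 1 − 0.995^36 = 16.5% |
| 1% | 1 − 0.99^36 = 30.4% |
| 2% | 1 − 0.98^36 = 51.7% |

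The description in Section 10.2 points towards the lower rows but does not fix a value.

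**The case against.** The strongest reply is that the endpoint does what the objective asks. The objective names the System, and a device-only count fits it on a narrow reading. Procedure-related SAEs are still rated, sent to the sponsor and reported with all other adverse events. Anesthesia tolerability is assessed before discharge and at 24 to 48 hours. Known intolerance to the anesthetic is an exclusion criterion (E-I). The plan sets no safety threshold or hypothesis, so 0/36 against 1/36 changes no study decision. On this view the choice is mainly one of presentation.

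Much of this stands, and it rules out several stronger readings that a reader might infer:

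- *Serious events are hidden or lost.* The commitment to report all adverse events excludes this for procedure-related events. For events before device use, Section 8.1 mentions only the medical record and does not say whether they also reach the study tables.
- *The endpoint contradicts the objective.* It does not.
- *Every procedure-caused event is excluded, whichever device grades count.* Table 5 allows Possible where concomitant therapy could be the cause, and Probable on a relevant time sequence alone. If those grades count, a reaction after device introduction could enter the endpoint.
- *The person who performed the treatment decides the attribution.* Section 8.2 says the investigator, and the documents do not state that this is the operator.

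What the reply does not remove is that the one result labelled as the safety endpoint omits an event assigned to the procedure alone.

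**Conclusion.** The point holds as a weakness in how the headline is defined. An SAE attributed to the procedure alone is outside the only safety endpoint, although the device is not used without that procedure. One such event would leave the headline at 0% (upper limit 9.7%), where a device-or-procedure endpoint would read 2.8% (0.07% to 14.5%).

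A reader might infer that the endpoint will understate the risk of treatment. The documents support only the conditional statement: the observed figure is lower if such an event occurs. The chance of that is 3.5% to 52% over assumed rates of 0.1% to 2%, and none of those rates comes from the plan. The calculation also assumes 36 treated subjects, independent events, and counting by subject.

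The change is worth making because it is cheap and makes the headline depend less on unblinded attribution between device and procedure. It does not remove all discretion, since an event can still be assigned to a pre-existing condition.

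**What to change.** 1. Define the safety endpoint as the number and percentage of treated subjects with at least one SAE through 1 month that is related to the device (Table 5) or to the study procedure (Table 6).
2. Name the relatedness grades that count, for both tables.
3. Show the device-related subset as a second line, with exact 95% confidence intervals on both lines.
4. Reconcile Section 8.1 with this, so that SAEs from the start of anesthesia are counted as procedure-related.
5. State in Sections 5 and 11 how a subject whose treatment is abandoned after anesthesia is handled in the safety set.

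**Cost.** Section 8.2 already requires both ratings, so the main change should need no new assessment. The adverse-event form is not among the documents, so the sponsor should confirm that it records both. The edits go beyond the endpoint sentence: Section 8.1 and the enrollment or safety-set wording must change too. The headline SAE rate can only stay equal or rise. The device-only figure remains available on the second line.

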4.6.2 Active Screening

At any time after the Subject has signed the necessary consent document, but before the NEUROMARK™ procedure subjects will perform eligibility assessments as outlined in **Table 1**. For additional details on the procedures below please refer to the Testing and Evaluation Guidelines document (**Appendix F**) The following must be completed at screening to assess subject eligibility:

- Collect and review medical history, demographics, and concomitant medications.
- Administer Baseline VAS NSS, rTNSS, mini-RQLQ.
- COVID-19 test for active infection.
- Pregnancy test for women of childbearing potential.
- Physical exam (height, weight, blood pressure, respiratory rate, heart rate and temperature).
- Evaluation of the nasal cavity by endoscopic assessment (recorded) to evaluate that the subject is an appropriate candidate for the NEUROMARK™ procedure. A Lund-Kennedy score should be assigned to each nostril.

If the results of the following assessment performed within 6 months prior to treatment are not in the subject's medical record, it must be collected as part of screening:

- Collection and/or review of CT scan of the paranasal sinuses. A Lund-Mackay Score should be assigned to each of the 12 sinuses. The sum of all scores is the Lund-Mackay Score.

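### The pregnancy test is required only at screening, so a negative result can be more than 14 days old at treatment, with no repeat listed in the pre-treatment check

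*Combined protocol and SAP*

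**What the plan says.** Section 4.6.2 (Active Screening) introduces its list with "The following must be completed at screening to assess subject eligibility". The list includes "Pregnancy test for women of childbearing potential" and, for efficacy, "Administer Baseline VAS NSS, rTNSS, mini-RQLQ". Screening may take place "At any time after the Subject has signed the necessary consent document" and before the procedure; no maximum length is given. The Screening Considerations in the synopsis add that, if a subject is ill, "the protocol required assessment or follow up visit may be postponed without a protocol deviation".

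Section 4.6.3 (Immediately Pre-Treatment) says that once screening is complete and all criteria are met, the procedure should be scheduled within 14 days unless the sponsor approves otherwise. Same-day screening and treatment is allowed. A final eligibility assessment is required, and four evaluations are listed: COVID-19 status, concomitant medications, physical exam and endoscopy. In Table 1 the pregnancy test is marked under Screening and nowhere else.

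Inclusion criterion I-C requires a negative pregnancy test, and exclusion criterion E-Q rules out pregnancy. Neither says how recent the test must be. Both 4.6.2 and 4.6.3 refer to Appendix F (testing and evaluation guidelines) for details; it is not in the text available for this review.

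On reuse of existing results, the synopsis has a general bullet: "If data are available at baseline and the information collected per protocol, the existing data may be used to support patient screening". Table 1 footnote 1 is specific to one test: "An existing CT scan may be used for the baseline assessment so long as it was performed within 6 months prior to treatment", provided that symptoms have stayed stable.

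**The concern.** A negative pregnancy test describes the day on which it was taken. The protocol uses it as an entry condition that has to hold at treatment, but no rule in the available text ties the test date to the treatment date. The only time limit nearby starts when the last screening item is finished, so any days between the pregnancy test and that point are not counted.

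Other criteria are anchored to treatment. The CT scan must fall within 6 months before it, E-L looks back 4 weeks from it, and I-I requires freedom from COVID-19 symptoms up to it. I-C has no such anchor. The investigator confirming eligibility on the treatment day may therefore have only an old result to rely on. What is at stake is the safety of a participant who became pregnant, or whose pregnancy became detectable, after the screening test. The statistical analysis is not affected.

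**Working it through.** **Step 1: what is refreshed on the day of treatment.** Table 1 set beside the list in 4.6.3:

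| Item | Table 1, Screening | Table 1, pre-treatment | 4.6.3 list |
|---|---|---|---|
| Physical exam | required | required | yes |
| Endoscopy | required | required | yes |
| Concomitant medications | required | required | yes |
| COVID-19 | test required | test optional | confirm no indication of infection |
| Pregnancy test | required where applicable | no mark | no |

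Four kinds of information are renewed or re-confirmed. The pregnancy test is not among them.

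**Step 2: the age of the test at treatment.** Let

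- s = days from the pregnancy test to completion of screening (no cap in 4.6.2);
- w = days from completion of screening to treatment (0 to 14 under 4.6.3);
- e = days added by a sponsor-approved extension (no cap in 4.6.3).

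Age at treatment = s + w + e.

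The protocol's own figure comes first. With s = 0, w = 14 and e = 0, the age is 0 + 14 + 0 = 14 days. The 14-day target therefore also limits the age of the test, but only if the test is taken on the day screening is completed and no extension is given. Without an extension, the age exceeds 14 days whenever s > 14 − w.

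| s | w | e | Age at treatment (days) |
|---|---|---|---|
| 0 | 0 | 0 | 0 (same-day treatment) |
| 0 | 14 | 0 | 14 |
| 1 | 14 | 0 | 15 |
| 7 (assumed) | 14 | 0 | 21 |
| 14 (assumed) | 14 | 0 | 28 |
| 30 (assumed) | 14 | 0 | 44 |

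An extension adds day for day: with s = 0 and w = 14, e = 1 already gives 15 days. The values of s are illustrations, because the documents do not say how long screening usually lasts. A gap is plausible where a subject has no CT from the previous 6 months and must obtain one before screening can be completed, or where an assessment is put off for illness.

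**Step 3: effect of a repeat rule.** If the test is repeated at the pre-treatment visit whenever s + w + e > 14, a repeated test has age 0 and an unrepeated one has age at most 14. The maximum becomes 14 days for every subject, whatever the length of screening or the extension.

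**Step 4: what cannot be calculated.** The documents give neither the expected number of women of childbearing potential among the 36 subjects nor a pregnancy rate, so no expected number of affected subjects is offered.

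**The case against.** The strongest objection is that test detail is delegated to Appendix F, which both sections already cite, so a window may exist there. This stands as a limit: the point concerns the available text only, and the fix gives way if Appendix F is as strict.

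Second, no passage makes a result invalid at day 15. That is correct. Fourteen days is the protocol's scheduling target, used here because the sponsor has already chosen it.

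Third, there are safeguards: the final eligibility assessment, the contraception requirement in I-D, and Section 11.1, which stresses that every treated patient must be eligible. They reduce the risk, but none supplies a new test result.

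A reader might also infer two stronger points, and neither is supported.

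- *That the synopsis contradicts 4.6.2 by letting sites reuse any old result.* The bullet covers only data collected as the protocol requires, and 4.6.2 requires the pregnancy test and scores at screening. Table 1 and footnote 1 follow shortly after the bullet in the same section. The texts can be read together.
- *That an old baseline score undermines the primary efficacy result.* The scores are subject to the same clock, but no consequence is shown. E-L partly covers the most obvious route, because it excludes a new sino-nasal regimen started within 4 weeks before treatment and not yet stabilized. I-L requires at least 6 months of symptoms, and E-V excludes purely seasonal allergy. Replacing the baseline in delayed subjects only would mix two baseline definitions in a paired analysis of about 36 subjects. A single screening baseline is defensible.

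**Conclusion.** The point holds for the pregnancy test. In the available text, a woman of childbearing potential can be treated on a negative result more than 14 days old: 15 days with a one-day gap and treatment on day 14, and 21 or 28 days with assumed gaps of 7 or 14 days. There is no upper limit once long screening or a sponsor extension is considered. This is possible rather than inevitable, since same-day treatment is allowed.

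The conclusion rests on two things: that Appendix F does not already set a window, and that the final eligibility assessment implies no new test beyond the evaluations listed. Severity is minor. This is a cheap safety improvement; it does not call the design or the efficacy analysis into question.

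**What to change.** In Section 4.6.3 and in the pre-treatment column of Table 1, add a pregnancy test for women of childbearing potential whose screening result is more than 14 days old on the day of treatment. State that this also applies when the sponsor extends the scheduling window, and that 14 days follows the protocol's scheduling target. If Appendix F already sets an equal or stricter window, no new rule is needed.

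Keep the single screening score as the baseline for all subjects. Naming the CT in the synopsis bullet on existing data would be an optional clarification.

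The cost is a few lines of protocol text and an occasional repeat test at a visit that already takes place. No visit is added, and the sample size and analysis do not change.
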